**Pregnancy tests (females of childbearing potential):**

- Urine  $\beta$ -HCG

Laboratory parameters will be presented in standard international (SI) units. The summaries will be based on central lab results only.

Quantitative results will be summarized for hematology, serum chemistry, and urinalysis parameters at each scheduled visit during the 24-week treatment period (Baseline, Weeks 2, 4, 8, 12, 16, 20 and 24) and at EOT. Both actual values and change from baseline will be summarized with descriptive statistics defined in [Section 11.1](#).

Clinical laboratory test values are markedly abnormal if they meet either the low or high markedly abnormal criterion listed in [Table 3](#). These criteria are based on lab normal ranges and discussions with the experts. The number and percentage of subjects with post-baseline markedly abnormal values will be summarized by parameter. The

Document: T:\PROJ\Shire\UYA25606\_Biostatistics\Documentation\SAP\SAP\SHP633-306\_SAP\_Final  
v2.0\_20180415.docx

Author: 

Version Number: Final V2.0  
Version Date: 15Apr2019

percentages will be calculated relative to the number of subjects with at least 1 post-baseline assessment for the associated parameter. The numerator is the total number of subjects with at least 1 post-baseline markedly abnormal value. A supportive listing of subjects with post-baseline markedly abnormal values will be provided including the subject number, site, parameter, lab dates, baseline, and post-baseline values. This listing will present all values for a subject and laboratory parameter if at least one post-baseline value for that subject and parameter is identified as being markedly abnormal.

**Table 3: Markedly Abnormal Laboratory Criteria**

Lab parameter	Unit	Lower Limit	Upper Limit
Chemistry			
Albumin	g/L	<=20	>=90
Alkaline Phosphatase	U/L	NA	>2*ULN
ALT	U/L	NA	>3*ULN
Amylase	U/L	<=15	>=350
AST	U/L	NA	>3*ULN
Bilirubin (total)	µmol/L	NA	>2*ULN
BUN	mmol/L	NA	>=10.7
Calcium (total)	mmol/L	<=2.1	>=3.0
Chloride	mmol/L	<=80	>=125
Cholesterol (total)	mmol/L	NA	>=12.9
Creatinine	µmol/L	NA	>=177
C Reactive Protein	mg/L	NA	>=21
Glucose	mmol/L	<=1.7	>=13.9
Gamma glutamyl transferase	U/L	NA	>100
Lipase	U/L	NA	>3*ULN
Magnesium	mmol/L	<LLN	>ULN
Phosphate	mmol/L	NA	>=2.0
Potassium	mmol/L	<=2.5	>=6.5
Sodium	mmol/L	<=120	>=165
Triglycerides	mmol/L	NA	>=5.6
Uric acid	µmol/L	NA	>=624 (males) >=505 (females)
Hematology			
Hematocrit	L/L	<=0.37 (males) <=0.32 (females)	>0.54 (males) NA (females)
Hemoglobin	g/L	<=115 (males) <=95 (females)	NA
Platelets	10  /L	<=75	>=700

Document: T:\PROJ\Shire\UYA25606\_Biostatistics\Documentation\SAP\SAP\SHP633-306\_SAP\_Final  
 v2.0\_20180415.docx

Author: [REDACTED]

Version Number:  
 Version Date:

Final V2.0  
 15Apr2019

White Blood Cells	10  /L	<=2.8	>=16.0
-------------------	--------------------	-------	--------

ULN = upper limit of normal

ALT = Alanine Aminotransferase, Equivalent to SGPT

AST = Aspartate Aminotransferase, Equivalent to SGOT

BUN = Blood Urea Nitrogen

Laboratory results will be presented in a listing for each lab panel (chemistry, hematology, and urinalysis) by subject, visit, and parameter. Laboratory values outside of the normal range will be flagged. Categorical urinalysis findings and urine pregnancy results will be presented in a listing only.

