APPENDIX 3 PARENTERAL NUTRITION/INTRAVEOUS ADJUSTMENT DURING TREATMENT PERIOD

Points to keep in mind when adjusting PN/IV volume during dosing:

- There will be no PN/IV reduction attempts at baseline and Week 1.
- Parenteral nutrition/intravenous reductions target urine output increases of at least 10% over baseline.
- Attempts to reduce PN/IV will be made at dosing Weeks 2, 4, 8, 12, 16, and 20.
- Parenteral nutrition/intravenous adjustments are targeted to be at least 10% but no more than 30% of **baseline** PN/IV level.
- Adjustments should be based on the actual PN/IV volume the subject infuses. Subjects should remain compliant with the PN/IV prescription during the length of the study.
- Parenteral nutrition/intravenous constituents may be adjusted at the discretion of the investigator.
- Criteria for PN/IV adjustments are in [Table A1](#).
- During the 48-hour I/O measurement period, oral intake should be consistent with baseline oral intake.
- If there is a change in oral intake, the investigator should consider this when adjusting the PN/IV volume.
- Subjects should be encouraged to maintain a stable normal or hyperphagic diet.
- Frequent checks will be made to ensure the adjustments are safe (see [Table A2](#)).
- Subjects who fail to maintain a PN/IV reduction due to a medical necessity (eg, sepsis or hospitalization due to an AE) will not be considered a failure of reduction.
- If at any time, the algorithm cannot be followed, consult with the sponsor's Medical Monitor.

Table A1 Parenteral Nutrition Adjustments at Scheduled Clinic Visits based on 48-hour Urinary Output

Urine Output	Parenteral Nutrition/Intravenous Action
Below 1.0 L/day or target based on stabilized urine output	Increase PN/IV by at least 10% (Week 2) or to previous level.
1.0 L/day or more and less than Baseline	If subject is dehydrated or inadequately nourished (see Table A2), increase PN/IV. If not, maintain PN/IV.
Baseline or more, and less than a 10% increase over Baseline	Maintain PN/IV
At least a 10% increase over Baseline	Reduce PN/IV by at least 10% of stabilized Baseline level up to a clinically appropriate amount (maximum of 30%).

L=liter; PN/IV=parenteral nutrition/intravenous (volume)

Table A2 Targeted Criteria for Hydration and Nourishment at all Clinic Visits and Interim Safety Visits

Hydration Assessment	Hydration Adequate
Hematocrit	At or below ULN
Serum BUN	At or below ULN
Serum creatinine	At or below 2xULN
Urine sodium	20 mmol/L or more

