Clinical signs and symptoms of dehydration	Absent
Body weight change in 4 weeks	Change less than 1.5 kg

BUN = blood urea nitrogen; ULN = upper limit of normal

Note: In combination with [Table A1](#), any one of the above criteria determines dehydration.

Steps for adjusting PN/IV volume:

1. **DOSING WEEKS 2, 4, 8, 12, 16, and 20:** Subjects will be assessed at planned intervals for hydration and nutrition. The subject will make all measurements of 48-hour I/O at home prior to the scheduled visits. Blood and urine samples will be collected to evaluate hydration and nutrition (see [Table A2](#)). All blood and urine samples should be taken at a consistent time period throughout the study, convenient for the subject and site staff.
2. **Parenteral Nutrition Changes:** Review [Table A1](#) and [Table A2](#) to take appropriate action.
3. **Interim Safety Evaluations:** If any PN/IV adjustments are made, the clinical effect and the health status of the subject will be assessed 5 to 7 days after the adjustment is implemented. Laboratory safety samples should be evaluated following a PN/IV adjustment (see [Table A3](#)), accompanied by determination of 48-hour I/O and symptoms of dehydration. At the interim safety visit, PN/IV should be increased if the decrease was not tolerated. No further reductions to PN/IV volume are made at the interim safety visit.

Table A3 Assessment of Tolerance of Pareneteral Nutrition/Intravenous Adjustments at Interim Safety Visits

Urine Output, Hydration and Nutrition	Pareneteral Nutrition/Intravenous Action
Output less than Baseline	Increase PN/IV to previous volume ^a
Baseline output or greater and subject is dehydrated (See Table A2)	Increase PN/IV to previous volume ^a
Baseline output or greater and subject is not dehydrated, but is inadequately nourished (See Table A2)	If possible, maintain PN/IV volume and increase nutrition. If not, increase PN/IV to previous volume ^a
Baseline output or greater and subject is adequately hydrated and nourished (See Table A2)	Maintain PN/IV

L=liter; PN/IV=parenteral nutrition/intravenous (volume)

^a If most recent reduction was greater than 10% due to a urine volume of more than 2 L/day, a more moderate increase in PN/IV is allowed.

4. Maintain the adjusted PN/IV level until the next scheduled visit.
5. Repeat steps 1 through 4 at each study visit as indicated per protocol.

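### SAP Table 3 sets a high-hematocrit limit for men only, so the markedly-abnormal summary and its listing cannot pick up a high value in a woman

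*SAP*

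**What the plan says.** SAP v2.0, Section 7.2, defines the flag as follows: "Clinical laboratory test values are markedly abnormal if they meet either the low or high markedly abnormal criterion listed in" Table 3. For the count, "The numerator is the total number of subjects with at least 1 post-baseline markedly abnormal value". For the denominator, "percentages will be calculated relative to the number of subjects with at least 1 post-baseline assessment for the associated parameter". The supportive listing prints a subject's values for a parameter only if at least one post-baseline value has been flagged.

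In Table 3 the hematocrit row has a lower limit for each sex, "<=0.37 (males) <=0.32 (females", but its upper limit is ">0.54 (males) NA (females". Hemoglobin has lower limits for both sexes and no upper limit for either. SAP v1.0 has the same entries. The SAP says that the criteria come from laboratory reference ranges and expert advice, and gives no reason for this cell.

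Protocol Table A2 (Appendix 2 of the original protocol, Appendix 3 of Amendment 1) lists what counts as adequate hydration at clinic and interim safety visits. One entry is "Hematocrit At or below ULN", with no restriction by sex. The note below the table says, in combination with Table A1, that "any one of the above criteria determines dehydration".

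**The concern.** Parenteral volume may be cut at Weeks 2, 4, 8, 12, 16 and 20. Hemoconcentration is thus a foreseeable effect of the study procedure, and the protocol monitors for it in every subject. The SAP's count of marked abnormalities covers it in men and leaves it out in women, within a single row and under a single percentage.

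The design of the table does not explain the asymmetry. Uric acid is the only other row with a sex-specific upper limit, and it sets one for each sex (624 and 505 µmol/L). The hematocrit row itself sets a lower limit for each sex. With no upper hemoglobin limit, no other red-cell row covers the gap.

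What is at stake is how one safety table is read. If no woman appears for high hematocrit, that is a property of the rule and not a finding, and nothing in the table tells the reader so.

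**Working it through.** The plan states no figure on this point, so there is none to reproduce. The check is to apply the rule as written.

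**Inputs (SAP v2.0, Table 3 and Section 7.2)**
- Male hematocrit: flagged if ≤0.37 or >0.54 L/L.
- Female hematocrit: flagged if ≤0.32 L/L; no upper limit.
- Numerator: subjects with at least one flagged post-baseline value, in either direction.
- Denominator: subjects with at least one post-baseline hematocrit.

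**Step 1: single values**

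| Sex | Hematocrit (L/L) | Flagged? |
|---|---|---|
| Female | 0.32 | yes (low) |
| Female | 0.45, 0.54, 0.55, 0.60, 0.70, 0.99 | no |
| Male | 0.37 | yes (low) |
| Male | 0.45, 0.54 | no |
| Male | 0.55, 0.60 | yes (high) |

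A woman's high value cannot be flagged at any level. It could be printed in the supportive listing only if she also had a value at or below 0.32.

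**Step 2: effect on the count (illustration on assumed data)**

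Take 5 assessed subjects, the planned minimum. Let k of them be women with a highest hematocrit of 0.60 and no low value, and let the other 5 − k be men at 0.42.
- Rule as written: the numerator is 0 for every k from 0 to 5, so the table shows 0 of 5.
- Any female limit that captured 0.60: the numerator is k, so the table shows k of 5.

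The value 0.60 only shows how the rule behaves. It is not a proposed limit, and the documents give no basis for choosing one.

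**Step 3: what else would show such a value**
- By-visit descriptive statistics include the minimum and maximum (Sections 7.2 and 11.1). These pool the sexes, so they do not show how many women were high.
- The general laboratory listing flags every out-of-range value (Section 7.2).
- New clinically significant results are to be reported as adverse events (protocol 7.2.3.1) and counted if treatment-emergent.
- Table 3 has upper limits that apply to both sexes for BUN (≥10.7 mmol/L), creatinine (≥177 µmol/L) and sodium (≥165 mmol/L).
- Urine output, oral intake and body weight are summarized separately.

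**The case against.** The strongest reply has four parts.

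**One-sided limits are normal here.** Of the 25 rows in Table 3, 13 have no lower limit, and hemoglobin has no upper limit. NA for females is an explicit entry and may be an expert's choice. This stands as a reason to ask and not to assume an error. It does not explain why one direction of one parameter is counted in one sex only.

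**Table A2 serves another purpose.** It guides adjustment of parenteral support, whereas Table 3 is a reporting threshold. The two also differ for creatinine (2×ULN against a fixed 177 µmol/L). That is right: there is no formal contradiction. Table A2 matters because it shows that the protocol regards high hematocrit as informative in women too.

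**The information is available elsewhere.** This is correct, as Step 3 shows, and with about 5 subjects the listings can be read in full. It limits the size of the point. A flag in a listing is still not a count.

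**The denominator is sound.** A reader might infer that women are wrongly kept in the denominator, or that the reportable high-hematocrit percentage is capped by the share of men. The SAP does not support either. It counts by parameter and in either direction, so a woman can enter the hematocrit numerator through a low value and belongs in the denominator. The SAP defines no separate high-hematocrit percentage.

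A reader might also extend the point to phosphate, which has an upper limit ("Phosphate mmol/L NA >=2.0") and no lower one, unlike the other electrolytes. That rests on symmetry alone. Low phosphate is not a Table A2 criterion, phosphate is not in the interim safety panel, and no section names low phosphate as a monitored risk.

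**Conclusion.** The point holds, within narrow limits. As written, the markedly-abnormal summary cannot count a high hematocrit in a woman, and the supportive listing cannot be triggered by one. No other red-cell row in Table 3 fills the gap, although the protocol treats hematocrit above ULN as a dehydration criterion for both sexes.

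The effect is exact for the individual (no flag at any high value) and cannot be sized for the trial, because the documents give neither a planned sex split nor an expected frequency. It matters only if at least one woman is treated, which the eligibility criteria allow. It does not touch efficacy, the other safety displays or the denominator. Saying that these values are never counted or never seen anywhere would overstate it.

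**What to change.** In SAP Table 3, replace the female NA in the hematocrit upper-limit cell with a value set by the sponsor's experts on the same basis as the male limit.

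If no female limit is agreed:
- Add a count, separately for each sex, of subjects with any post-baseline central-laboratory hematocrit above the sex-specific ULN. The denominator is subjects of that sex with at least one post-baseline hematocrit. One criterion then serves both sexes, and it matches Table A2. This assumes that the central laboratory reports sex-specific ranges, which the documents do not state.
- Footnote the hematocrit row to say that the 0.54 limit applies to males only.

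If the NA is intended, the SAP should give the reason and still carry the footnote.

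The cost is two or three lines of programming and possibly a slightly less favorable safety count. No new data are needed, because hematocrit is already in the central panel. Limits based on the reference range are already used in Table 3 (magnesium), and v2.0 already reopened the table to add white blood cells. One limit remains: SAP laboratory summaries use central results only, and tests 5 to 7 days after a change in parenteral support may be run at the site, so neither version of the fix would count those.

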### 7.3 Vital Signs, Body Weight and BMI

The descriptive statistics defined in [Section 11.1](#) will be used to summarize the vital signs (i.e., systolic blood pressure, diastolic blood pressure (mmHg), pulse rate, body temperature, weight, and BMI) by scheduled visit during the 24-week treatment period (Baseline, Weeks 2, 4, 8, 12, 16, 20 and 24) and at EOT for the Safety Population. Both actual values and changes from baseline will be summarized.

### 7.4 Electrocardiogram

The number and percentage of subjects with each type of ECG finding (Normal/Abnormal, Not Clinically Significant/Abnormal, Clinically Significant) will be presented at Baseline, Weeks 4 and 24, and EOT for the Safety Population. All ECG data will be listed.

### 7.5 Other Safety Data

#### 7.5.1 Physical Examination

Physical examination results will be presented in a listing only.

#### 7.5.2 Antibodies to Teduglutide

A summary table will provide the number of subjects with a sample analyzed for Baseline, Weeks 12, 24 and EOT. The summary table will also provide the number of subjects with an antibody finding at each of those visits in the Safety Population.

All antibody data including neutralizing antibodies and antibody titers will be listed.

### 7.5.3 48 Hour Oral Fluid Intake and Urine Output

Oral/enteral intake and urine output measurements collected during 48 hours prior to each visit will be summarized by scheduled visit during the 24-week treatment period (Weeks 2, 4, 8, 12, 16, 20 and 24) and at EOT. Oral/enteral intake and urine output measurements for Day 1 and Day2 will be captured in the eCRF. The average of Day 1 and Day 2 measurement in mL will be summarized.

Actual values and both absolute and percent change from baseline will be summarized in the Safety Population with descriptive statistics defined in Section 11.1.

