7.2.3.6 Gastrointestinal-specific Testing

Gastrointestinal testing will be done for all subjects during the screening period. Follow-up testing will be performed as necessary according to the guidelines noted below.

Colonoscopy/Sigmoidoscopy

A colonoscopy/sigmoidoscopy of the remnant colon with polyp removal will be performed prior to teduglutide exposure (during stabilization if not completed within 6 months prior to screening) in subjects with any colon remnant including a rectal stump. This will be repeated at Visit 10 (or early termination). The date and result of colonoscopy are to be recorded in the eCRF.

Abdominal Ultrasound

An abdominal ultrasound will be performed prior to teduglutide exposure (during stabilization) if this procedure was not performed during the 6 months prior to screening (however, the results of the procedure must be documented).

Upper GI Contrast Series with Small Bowel Follow-through

Upper GI contrast series with small bowel follow-through will be required for all subjects with a history of Crohn's disease and will be performed during the stabilization period, prior to the baseline visit.

Esophagogastroduodenoscopy

Esophagogastroduodenoscopy (EGD) will be performed on all subjects prior to teduglutide exposure (during the stabilization period if not completed within 6 months prior to screening). Esophagogastroduodenoscopy will be repeated at Week 24/Visit 10 (or ET) for subjects with any of the following risk factors:

- Age 40 or over at Week 24/Visit 10/ET
- History of H pylori gastritis
- History of atrophic gastritis
- History of intestinal metaplasia or dysplasia in the stomach

For subjects that do not have any of the above risk factors, EGD may be repeated at Visit 10/ET at the discretion of the investigator. The dates and results of all EGDs are to be recorded in the eCRF.

48-Hour Oral Fluid Intake and Urine Output

Subjects will be provided with urine collection containers (as needed) in order to collect 48-hour urine during the 2 days prior to study visits as required. The center staff will contact the subject at least 48 hours before the scheduled visits to remind the subject to start measuring I/O, and to record these measurements into the diary. During the 48-hour measurements, the subject should maintain their usual oral fluid intake. 48-hour urine output measurements will also be collected prior to all interim safety visits.

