9.8 Safety Analyses

The safety endpoints include AEs, 12-lead ECG, vital signs, laboratory safety data, antibodies to teduglutide, and 48-hour urine output, body weight, BMI and gastrointestinal-specific tests.

Adverse events will be coded using the Medical Dictionary for Regulatory Activities (MedDRA). Treatment-emergent AEs are defined as AEs that started or worsened on or after the date and time of the first dose of study dose. Treatment-emergent AEs will be summarized by system organ class and preferred term using descriptive statistics (eg, number and percentage of subjects). Adverse events will be summarized by severity, relationship to treatment, and for AEs leading to discontinuation, and death. In addition, SAEs will also be tabulated by overall and treatment-related events.

For laboratory tests, 48-hour urine output, vital signs, body weight, body mass index, and ECG variables, descriptive statistics (eg, n, mean, standard deviation, median, minimum and maximum values, the number and percentage of subjects in specified categories) will be used to summarize the absolute values and change from baseline at each time point.

The number and percentage of subjects classified as having antibodies to teduglutide will be used to summarize the presence of antibodies.

The safety population will be the analysis population for all the safety data analysis.

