### **3.4 Sample Size and Power Considerations**

The sample size of the SHP633-306 study is based on patient prevalence and study design elements; no statistical estimation was involved. Possible medical institutes for SBS studies are limited, given the rarity of the disease and the very limited number of patients with SBS (<1000) in Japan. The applicant considers that 5 treated subjects in SHP633-306 should provide sufficient basic information concerning the efficacy, safety and tolerability as well as PK of teduglutide in the Japanese study population.

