## 6.1 Analyses of Efficacy Endpoints

The efficacy endpoints are the following:

- Absolute and relative change from baseline in weekly PN/IV volume by visit and at EOT.
- Percentage of subjects who achieve at least 20% reduction from baseline in weekly PN/IV volume at both Weeks 20 and 24.
- Percentage of subjects who achieve at least a 20% reduction from baseline in weekly PN/IV volume at each visit
- Change in days per week of PN/IV support from baseline by visit.
- Change in plasma citrulline from baseline by visit.
- Number of subjects who were able to completely wean off of PN/IV support.

Analyses on weekly PN/IV support are based on two data sources: the subject diary data and the investigator prescribed data.

The diary weekly PN/IV volume will be calculated based on the daily volumes recorded in subjects' diaries within 14 days prior to each scheduled visit. The calculation will follow the formula below.

Weekly volume = (sum of daily volumes in the diary/number of days with values) \*7

Missing daily PN/IV volumes will not be imputed. A maximum of 5 missing days (or at least 9 days of non-missing data) from the 14-day intervals are allowable, otherwise the interval will be classified as missing. One exception to this rule is the baseline interval, which will be filtered back up to 28 days prior to first dose until 9 data points are obtained.

Investigator prescribed data is captured in the PN/IV baseline and PN/IV adjustment in eCRF. Investigator prescribed weekly PN/IV volume reported at each visit will be the most recent PN/IV prescription (from either baseline or prescription adjustments) prior to or on the date of visit.

Data will be summarized at all scheduled visits during the 24-week treatment period. An EOT time point will also be added. Therefore,

Document: T:\PROJ\Shire\UYA25606\_Biostatistics\Documentation\SAP\SAP\SHP633-306\_SAP\_Final  
v2.0\_20180415.docx

Author: [REDACTED]

Version Number:  
Version Date:

Final V2.0  
15Apr2019

- PN/IV weekly volume and days per week of PN/IV support will be summarized at Baseline, Weeks 2, 4, 8, 12, 16, 20, 24 and EOT.
- Plasma citrulline will be summarized at Baseline, Weeks 4, 8, 16, 24 and EOT.

Datasets and listings will include data collected at unscheduled visits. Data collected at unscheduled visits will not be included in summaries by timepoint or visit unless specified otherwise.

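### The SAP's urine-output table leaves out interim safety visits, so falls in output found and reversed there after a PN/IV reduction are not summarised

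*SAP*

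**What the plan says.** Urine output over 48 hours is a safety endpoint in Protocol 9.8 and SAP 2.3.2. SAP v2.0 7.5.3 says the measurements "will be summarized by scheduled visit during the 24-week treatment period" and lists the time points as "Weeks 2, 4, 8, 12, 16, 20 and 24) and at EOT". The daily average of Day 1 and Day 2 is summarised, with absolute and percent change from baseline, using the continuous statistics of SAP 11.1. Section 7.5.3 mentions neither interim visits nor a worst value.

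Two general rules point the same way. SAP 6.1 says "Data collected at unscheduled visits will not be included in summaries by timepoint or visit unless specified otherwise". SAP 11.4 also keeps unscheduled measurements out of by-visit summaries, but lets them contribute to EOT. Both rules stand in efficacy sections.

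The protocol collects more than the table uses. Section 7.2.3.6 states that "48-hour urine output measurements will also be collected prior to all interim safety visits". Under Amendment 1, Appendix 3, "Attempts to reduce PN/IV will be made at dosing Weeks 2, 4, 8, 12, 16, and 20", and each adjustment is checked 5 to 7 days later. There, "At the interim safety visit, PN/IV should be increased if the decrease was not tolerated". In Table A3, output under Baseline is itself a trigger for the increase. The resulting volume is then held to the next scheduled visit.

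**The concern.** The interim collection is the one taken to test whether a change in PN/IV was tolerated. If it shows a fall, the protocol acts at once, and the next value that reaches the table is measured under the raised volume. A subject could have one or more reductions fail in this way while the by-visit means, medians and minima look steady.

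The planned sample is at least five treated subjects, so a single unsummarised failure is a material part of what the study can say about hydration during weaning.

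Other planned outputs do not reliably fill the gap. Protocol 7.2.3.1 allows interim laboratory tests to be run at the site, while SAP 7.2 summarises central results only, so locally run interim haematocrit, BUN, creatinine and urine sodium also miss the tables. Under Protocol 8.1.4, disease symptoms within normal fluctuation need not become adverse events.

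**Working it through.** The plan gives no figure to reproduce: the study is descriptive, and on sample size SAP 3.4 says "no statistical estimation was involved". The check is a timeline.

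**Inputs**
- Summarised weeks: 2, 4, 8, 12, 16, 20, 24, plus EOT (SAP 7.5.3).
- Weeks at which a reduction may be made: 2, 4, 8, 12, 16, 20 (Protocol Amendment 1, Appendix 3).
- Interim visit on day d after the change, d = 5 to 7 (Appendix 3, step 3).
- Each output value covers the 2 days before the visit (Protocol 7.2.3.6).
- Visit windows of 2 to 7 days (SAP 11.3). The width at each visit cannot be read from the supplied Table 2.

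**Nominal days.** Assume the change takes effect on the visit day.

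Days from interim visit to start of next summarised collection = 7 × (next scheduled week − week of reduction) − d − 2.
- Week 2 reduction, next visit Week 4: 14 − 5 − 2 = 7 and 14 − 7 − 2 = 5, so 5 to 7 days.
- Reductions at Weeks 4, 8, 12, 16 and 20, next visit four weeks later: 28 − 5 − 2 = 21 and 28 − 7 − 2 = 19, so 19 to 21 days.

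On nominal days the next summarised collection therefore always starts after the interim visit.

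**Visit windows.** Take d = 7 and move the two scheduled visits towards each other by w days each.
- Week 2 to Week 4: 14 − 2w − 7 − 2. With w = 2 this is 1 day; with w = 3 it is −1 day. From ±3 days the Week 4 collection can begin before the interim visit and may catch output before PN/IV is raised.
- Four-week intervals: 28 − 2w − 7 − 2. With w = 2 this is 15 days; with w = 7 it is still 5 days.

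**What still reaches the table**
- Low output first found at a scheduled visit. It is measured over the 48 hours before that visit, hence before any increase under Table A1.
- Output on reductions that were tolerated and left in place.
- An interim value at EOT, if it is the subject's last available measurement (SAP 11.4).
- The residue of a partial reversal. A footnote to Table A3 permits a smaller increase in one case.

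**The case against.** The strongest reply is that summarising by scheduled visit is conventional in a small descriptive study and contradicts no protocol requirement. SAP 6.1 sends unscheduled data to datasets and listings, prescription changes are captured in the eCRF, and with about five subjects the listings will be read line by line. Table and listing specifications are in a separate document not supplied here, so the absence of an intake/output listing cannot be inferred. All of this stands. It makes the point an improvement rather than an error, but none of these routes is a summary of interim urine output.

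A reader might also infer more than the documents support:
- *That the table shows only values after correction.* It does not. Table A1 acts on output measured before the scheduled visit, and those lows are tabulated, as are tolerated reductions.
- *That a fixed share of collections is lost.* No share can be given. A reduction needs output at least 10% over Baseline, so some attempts produce none. Protocol 7.2.2.2 requires an interim visit after any physician-directed volume change, so increases add visits too.
- *That Protocol 9.8 requires a categorical count.* The words "the number and percentage of subjects in specified categories" close a list of examples shared by several safety variables, and no urine-output categories are set.
- *That low output means dehydration.* Table A2 judges dehydration on other criteria, and Table A3 treats the two in separate rows.

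Finally, because reductions start from raised output, some return towards Baseline is expected, and eligibility itself tolerates ±25% variation in 48-hour volumes. Any count of interim values below Baseline will include ordinary variation and should be labelled so.

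**Conclusion.** The point holds as a gap in reporting. Falls in output that are found and reversed at an interim safety visit do not enter the by-visit table, except possibly through EOT, so the table can understate falls after PN/IV reductions.

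For reductions from Week 4 onwards the separation survives even ±7-day windows. For the Week 2 reduction it holds on nominal days and can be lost from ±3 days. These figures assume that the change takes effect on the visit day and that the interim visit falls on day 5 to 7.

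How often a reversed fall will occur cannot be derived from the documents. Nor do they say outright that interim intake and output values are entered in the eCRF. The conclusion concerns reporting only and takes no position on the PN/IV adjustment rules.

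**What to change.** Keep the by-visit table. Add to SAP 7.5.3 one descriptive table for the Safety Population over all on-treatment 48-hour collections, interim visits included, giving:
- each subject's lowest output, as the Day 1/Day 2 average, and its change from Baseline;
- the number and percentage of subjects with any value below 1.0 L/day, the level already used in Table A1 (the averaged values compare with it directly);
- the number and percentage with any interim value below Baseline, the Table A3 trigger, with a footnote that this includes ordinary variation;
- the number of PN/IV reductions reversed at an interim visit.

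This follows the approach of SAP 7.2, which already counts subjects with any markedly abnormal post-baseline laboratory value. The sponsor should confirm that interim intake and output values are entered in the eCRF.

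The cost is one extra table, a few lines of SAP text, and some counts that reflect normal variation. It uses measurements the protocol already requires and changes nothing in patient care.
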